**NOVUM PHARMACEUTICAL RESEARCH SERVICES**  
**STATISTICAL ANALYSIS PLAN**

**Novexatin 10% topical solution**

**Protocol / Study No. NVXT 1404/71442603**

**8.3.2 Vital Signs**

The patient's vital signs will be recorded (heart rate, blood pressure, temperature and respiration rate) at Visits 1, 3, 5, 6 and 7.

Descriptive summaries (number of observations, mean, standard deviation, minimum, median and maximum) will be provided by treatment group and visit.

**8.3.3 Clinical Laboratory Results**

Clinical laboratory results (hematology, chemistry and urinalysis) will be collected at Visits 1, 3 and 7.

Descriptive summaries (number of observations, mean, standard deviation, minimum, median and maximum) will be provided by treatment group and visit.

All data will be listed by treatment group and visit.

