Statistical Analyses	
Safety: All safety parameters will be listed and summarized descriptively. Changes from baseline will be calculated, if appropriate.
 
Efficacy: In order to preserve an overall type-I error (alpha) of 5%, a hierarchical evaluation scheme for evaluation of complete and almost complete therapeutic cure, complete and satisfactory clinical cure and mycologic cure will be employed for the primary and secondary endpoints. The four comparisons of interest for the primary endpoint and the secondary endpoints -1 and -2 are:
 
 1. Group B versus Group C – at the test-of-cure visit at Day 365 2. Group A versus Group C – at the test-of-cure visit at Day 365 3. Group B versus Group A – at the test-of-cure visit at Day 365 4. (Group A + Group B) versus Group C – at the test-of-cure visit at Day 141

A Randomized, Placebo-Controlled, Double-Blind, Parallel-Group, Multi-Site Phase 2b Clinical Study to Assess the Efficacy, Safety and Tolerability of 8-Week Regimens of Novexatin®, 10% Topical Solution (Taro Pharmaceuticals, USA, Inc.) in Patients with Mild to Moderate Onychomycosis

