### **8.3 Safety Analysis**

All study patients who are randomized to the active treatment period of the study, and received study product will be included in the comparative safety analysis. The safety profile of each treatment group will be evaluated by comparing adverse events, application site reactions, vital signs and changes in clinical laboratory results obtained throughout the study. Data will also be collected during the study to compare the results of the KOH stains to the mycological culture results observed during the study.

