|                  | 7     |               |                           |                           |                           |

Hematocrit (L/L)  
etc

Treatment Group A: Novexatin® 10% Topical Solution for Days 1 – 56 and Placebo (Vehicle) Topical Solution for Days 281 – 336

Treatment Group B: Novexatin® 10% Topical Solution for Days 1 – 56 and Days 281 – 336

Treatment Group C: Placebo (Vehicle) Topical Solution for Days 1 – 56 and Days 281 – 336

Source: Listing L16.2.8.1  
Created on: ddmmmyy hh:mm

Page 1 of N

**T14.3.7 Summary of Clinical Laboratory Testing (Chemistry)  
(Safety Population)**

**T14.3.8 Summary of Clinical Laboratory Testing (Urinalysis)  
(Safety Population)**

**T14.3.9 Summary of Frequency of Application Site Reactions  
(Safety Population)**

| Signs and Symptoms | Visit | Scale    | Treatment Group A
N=xx | Treatment Group B
N=xx | Treatment Group C
N=xx |
|--------------------|-------|----------|---------------------------|---------------------------|---------------------------|
| Erythema (redness) | 3     | Absent   | xxx (xx.x%)               | xxx (xx.x%)               | xxx (xx.x%)               |
|                    |       | Mild     | xxx (xx.x%)               | xxx (xx.x%)               | xxx (xx.x%)               |
|                    |       | Moderate | xxx (xx.x%)               | xxx (xx.x%)               | xxx (xx.x%)               |
|                    |       | Severe   | xxx (xx.x%)               | xxx (xx.x%)               | xxx (xx.x%)               |
|                    | 4     |          |                           |                           |                           |
|                    | 5     |          |                           |                           |                           |
|                    | 6     |          |                           |                           |                           |
|                    | 7     |          |                           |                           |                           |
| Scaling/Dryness    |       |          |                           |                           |                           |
| Stinging/Burning   |       |          |                           |                           |                           |
| Erosion            |       |          |                           |                           |                           |

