**L16.2.8.1 Listing of Clinical Laboratory Testing Results (Hematology)**

| Treatment Group   | Patient Randomization Number | Visit | Date       | Lab Test   | SI Results | SI Unit | Normal Range |
|-------------------|------------------------------|-------|------------|------------|------------|---------|--------------|
| Treatment Group A | xx-xxxx                      | 1     | yyyy-mm-dd | Hemoglobin | xxx        | g/L     | xxx, xxx     |
|                   |                              | 3     | yyyy-mm-dd | Hemoglobin | xxx        | g/L     | xxx, xxx     |
|                   |                              | 7     | yyyy-mm-dd | Hemoglobin | xxx        | g/L     | xxx, xxx     |

Treatment Group B

Treatment Group C

---

Treatment Group A: Novexatin® 10% Topical Solution for Days 1 – 56 and Placebo (Vehicle) Topical Solution for Days 281 – 336

Treatment Group B: Novexatin® 10% Topical Solution for Days 1 – 56 and Days 281 – 336

Treatment Group C: Placebo (Vehicle) Topical Solution for Days 1 – 56 and Days 281 – 336

Created on: ddmmmyy hh:mm

Page 1 of N

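### The plan promises a comparison of changes in laboratory results, but SAP 8.3.3 specifies only by-visit summaries: no change from Visit 1, no shift table, no count of patients who become abnormal

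*SAP*

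**What the plan says.** **The stated comparison.** SAP 8.3 says the safety profile of each group will be evaluated by comparing adverse events, "application site reactions, vital signs and changes in clinical laboratory results obtained throughout the study". Protocol 9.1, Protocol 10.6 (Safety Analysis) and SAP 3 say the same in substance. The protocol synopsis adds, for safety parameters generally: "Changes from baseline will be calculated, if appropriate".

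**The planned summary.** SAP 8.3.3 states: "Clinical laboratory results (hematology, chemistry and urinalysis) will be collected at Visits 1, 3 and 7". The analysis is then: "Descriptive summaries (number of observations, mean, standard deviation, minimum, median and maximum) will be provided by treatment group and visit". Shell T14.3.6 (hematology) follows this, with n, mean ± SD, median and range at Visits 1, 3 and 7. T14.3.7 (chemistry) and T14.3.8 (urinalysis) are given as titles only.

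**The patient-level data.** SAP 8.3.3 also says: "All data will be listed by treatment group and visit". The shell for L16.2.8.1 has one row per patient, visit and test, ending in the columns "SI Results | SI Unit | Normal Range". It has no abnormality flag and no change column. Chemistry and urinalysis listings are planned under L16.2.8.2 and L16.2.8.3.

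**Departures from the protocol.** SAP 8.7 covers the change of efficacy test, the ITT wording and the additional analyses. It does not mention laboratory summaries.

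**The concern.** A comparison of changes needs each patient's later value set against that patient's own Visit 1 value. Summaries made separately at each visit do not do this. The difference between two visit means equals the mean patient change only if the same patients contribute at both visits, and even then the spread of changes is lost.

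For laboratory safety the useful questions are how many patients moved from normal to abnormal, and whether that number differs between Groups A, B and C. The planned tables answer neither. If a few patients in one group changed, the tables could look unremarkable and the imbalance would surface only if someone tallied the listings by hand.

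Urinalysis raises a second, smaller problem. A mean and SD are prescribed for a panel that includes tests such as nitrite, leukocyte esterase, occult blood and protein. If these are reported as categories, a mean has no meaning.

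**Working it through.** The documents give no laboratory figure to reproduce. The check is a comparison of texts, followed by an illustration on assumed values.

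**1. Promise against output**

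| Item | Stated aim (Protocol 9.1, 10.6; SAP 3, 8.3; synopsis) | SAP 8.3.3 and T14.3.6–8 |
|---|---|---|
| Change from Visit 1 | Changes in laboratory results to be compared; change from baseline where appropriate | None |
| Shift against normal range | Not promised by name | None |
| Count outside normal range | Not promised by name | None |
| By-visit n, mean, SD, median, minimum, maximum | – | Yes |
| Individual values with normal range | – | Yes, in listings |

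The first row is the mismatch. The next two are standard ways to make the promised comparison, not separate commitments.

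**2. What the planned statistics would and would not show**

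Inputs: n = 60 per group (enrolment ceiling, SAP 5). Assumed, because the documents give no laboratory values: creatinine averages 0.9 mg/dL in the other patients, SD 0.15, upper limit of normal 1.2.

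Formula for k patients at value x: mean = ((n − k) × 0.9 + k × x) / n.

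*Values above the range, x = 1.8:*
- k = 1: (59 × 0.9 + 1.8) / 60 = 0.915
- k = 3: (57 × 0.9 + 3 × 1.8) / 60 = 0.945
- SD, with p = k/60: √(0.15² + p(1 − p) × 0.9²), where the last 0.9 is 1.8 − 0.9. This gives √(0.0225 + 0.0133) = 0.19 for k = 1 and √(0.0225 + 0.0385) = 0.25 for k = 3.
- If 1.8 is the highest value, the maximum is 1.8 in both cases.

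The mean moves little, the SD rises and the maximum signals that something is there. But the maximum is the same for one affected patient as for three, and it does not say whether the value was already high at Visit 1. Baseline abnormality is possible, since exclusion criterion 12 bars abnormal laboratory values only where the Investigator judges them disqualifying.

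*A rise that stays inside the range, 0.60 to 1.15, in one patient:*
- Before: (59 × 0.9 + 0.60) / 60 = 0.895
- After: (59 × 0.9 + 1.15) / 60 = 0.904

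If another patient is already at or above 1.15, the maximum does not change. Only that patient's rows in the listing would show the rise.

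**3. Size of the listing**

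Protocol Appendix D has 14 chemistry tests. At 3 visits and up to 180 patients: 14 × 3 × 180 = 7,560 rows, for chemistry alone.

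**4. Who is in each visit mean**

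The sample-size section allows 23% drop-out: 60 × 0.23 = 13.8, about 14 patients per group who could be in the Visit 1 mean but not in the Visit 7 mean. This is an upper bound. Visit 7 doubles as the early-termination visit and includes laboratory tests (Protocol 9.5.7), and all efforts are to be made to complete it for early terminators (Protocol 9.3.5). The SAP does not say whether those values enter the Visit 7 summary.

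**5. Urinalysis**

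SAP 8 prescribes number and percent for categorical variables. SAP 8.3.3 names urinalysis among the laboratory results and prescribes mean and SD. For a urine test reported as a category, both rules cannot be followed. Appendix D does not state the result format, so the conflict is conditional on it.

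**The case against.** The strongest reply is that little is lost. The tables carry minimum, median, maximum and SD as well as the mean, every value is listed beside its normal range, and the shells are declared to be a general layout open to modification. Clinically noted changes can also be reported as adverse events (Protocol 9.7 and 9.7.1), which are counted by patient and preferred term. The synopsis leaves change from baseline to discretion, and no document promises shift tables or abnormal counts. For urinalysis, the general categorical rule in SAP 8 is already available.

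Much of this stands, and it rules out several stronger readings that a reader might infer:
- *That only means are tabulated, or that individual abnormalities cannot show.* They can, through the range and the listings.
- *That a kidney or liver signal is being hidden.* The tubule finding in Protocol 7.3 appears in the account of intravenous dosing in rats, above the NOAEL. Human plasma levels were below quantitation (Protocol 7.4). No liver finding for novexatin is described.
- *That 14 of 60 patients per group will be absent at Visit 7.* That is a ceiling, as shown above.
- *That vital signs have the same contradiction.* In SAP 8.3 the word for change attaches to laboratory results, not to vital signs.

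What does not stand is that these outputs deliver the stated comparison. A maximum is one number per group and visit, and a listing is not a comparison of groups. No rule makes every out-of-range value an adverse event. The discretion in the synopsis is never exercised: the SAP nowhere says that change from baseline is inappropriate. The freedom to modify shells does not alter the text of 8.3.3.

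**Conclusion.** The point holds as a gap between a stated method and its specification. Followed as written, SAP 8.3.3 yields no within-patient change and no between-group count of patients who become abnormal, although both documents name change in laboratory results as a basis for judging safety. SAP 8.7 gives no reason. For urinalysis, 8.3.3 and SAP 8 conflict for any test reported as a category.

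The consequence is limited to safety reporting; the efficacy analyses are untouched. The data are collected and listed, so nothing is irrecoverable, and the documented low systemic exposure makes the prior risk small. The numerical illustration rests on assumed creatinine values and shows only how such patterns behave in the planned tables, not that any are expected. The change is still worth making, because it is cheap and this phase 2b trial has placebo and two regimens to compare.

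**What to change.** In SAP 8.3.3 and the shells:

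- **T14.3.6 and T14.3.7:** add change from Visit 1 to Visit 3 and from Visit 1 to Visit 7, in patients with both values. Visit 7 is the only scheduled laboratory sample after the second course.
- **Shift tables by group:** low/normal/high from Visit 1 to Visit 3, to Visit 7 and to the worst post-baseline value, using the normal ranges already in L16.2.8.1.
- **T14.3.8:** for urine tests reported as categories, replace means by n (%) per category, with the same shift. Name the tests concerned.
- **Early termination:** state whether laboratory values from early-termination visits enter the Visit 7 summary.

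An abnormality flag in the laboratory listings would help but is not essential. Change from Visit 1 for vital signs (T14.3.5) is optional, since it follows only from the discretionary sentence in the synopsis. If the sponsor prefers to keep the present tables, SAP 8.7 should say so and why.

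The cost is SAP wording and a little extra programming. No new data, visits or samples are needed.

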**8.3.4 Application Site Reactions**

At Visits 3, 4, 5, 6 and 7, the Investigator will examine the treatment area and complete the signs and symptoms of irritation assessment.

A frequency summary table comparing the application site reactions for each treatment group will be presented by visit.

All data will be listed by treatment group and patient.

**8.3.5 Evaluation of Toenail Condition/Appearance:**

The toenail, one of the two great toenails, that the investigator considers to be the most appropriate as the target toenail will be identified and designated as the "target toenail" at Visit 2 and used for evaluations.

The overall appearance of the target toenail over time will be monitored during the study:

1. Self-assessed by patients. The results of the self-assessment will be recorded by the patient before beginning therapy at Visit 2 and at all subsequent visits. Patients will use a 5-point scale (see Appendix A) for target toenail appearance.
2. Assessed by Investigator: Investigators will rate the status of the target toenail before beginning therapy at Visit 2 and at all subsequent visits. Nail condition/appearance by investigator will be evaluated after nail trimming to the distal groove and before further trimming, if required, for the mycological evaluation. Investigators will use a 5-point scale (see Appendix A) target toenail appearance.

**NOVUM PHARMACEUTICAL RESEARCH SERVICES  
STATISTICAL ANALYSIS PLAN**

**Novexatin 10% topical solution**

**Protocol / Study No. NVXT 1404/71442603**

A frequency summary table for each treatment group will be presented by visit.

All data will be listed by treatment group, patient, and evaluation day.

**8.4 Multiple Comparisons**

No multiple comparison adjustment will be made in this study other than the pre-defined hierarchical testing for the primary and secondary endpoints.

**8.5 Methods for Handling Missing Data**

For demographic and baseline characteristics, each variable will be analyzed using all available data. Patients with missing data will be excluded only from analyses for which data are not available.

The following rules and conventions will be used for patients who terminate from the study early or are dropped from the study because of protocol deviations.

Any patient who either requests to be dropped from the study because of lack of therapeutic efficacy or is dropped by the Investigator for lack of therapeutic efficacy will automatically be considered a "clinical failure" regardless of their target toenail assessment score at the termination visit.

Any patient who uses any protocol restricted medication specifically for the treatment of their infection will be discontinued from further participation in the study and automatically be considered a "clinical failure" regardless of their target toenail assessment score at the last visit.

Any patient who uses any protocol restricted medication NOT specifically for the treatment of their onychomycosis will be discontinued from further participation in the study. The patient will be considered a "clinical cure" or "clinical failure" based on the target toenail assessments at the termination visit.

Any patient who is dropped for any reason other than those covered above will be included in the ITT, provided they had a positive baseline culture and applied at least one dose of the study product. Examples would include: failure to use the study products as required by the protocol, patient withdraws consent for continued participation, patient fails to make study visits on a timely basis.

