Efficacy Endpoints	
The primary endpoint is the proportion of patients in each treatment group with a complete therapeutic cure of onychomycosis of the target toenail assessed at each of the two test-of-cure visits (Day 141 and Day 365).
 
The secondary endpoint-1 is the proportion of patients in each treatment group with a complete or almost complete therapeutic cure of onychomycosis of the target toenail assessed at each of the two test-of-cure visits (Day 141 and Day 365).
 
The secondary endpoint-2 is the proportion of patients in each treatment group with a mycological cure of the target toenail assessed at each of the two test-of-cure visits (Day 141 and Day 365).
 
The secondary endpoint-3 is the proportion of patients in each treatment group with a complete clinical cure of the target toenail assessed at each of three test-of-cure visits (Day 141, Day 281 and Day 365).
 
The secondary endpoint-4 is the proportion of patients in each treatment group with a satisfactory clinical cure of the target toenail assessed at each of three test-of-cure visits (Day 141, Day 281 and Day 365).
 
Complete therapeutic cure is defined as both complete clinical and mycological cure of the target toenail
 
Almost complete therapeutic cure is defined as both mycological and satisfactory clinical cure of the target toenail
 
Mycological cure is defined as a negative KOH test and a negative fungal culture.
 
Complete clinical cure is defined as 0% nail involvement.
 
Satisfactory clinical cure is defined as $\leq 5\%$ of the target toenail involvement.

A Randomized, Placebo-Controlled, Double-Blind, Parallel-Group, Multi-Site Phase 2b Clinical Study to Assess the Efficacy, Safety and Tolerability of 8-Week Regimens of Novexatin®, 10% Topical Solution (Taro Pharmaceuticals, USA, Inc.) in Patients with Mild to Moderate Onychomycosis

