9.3.5 Early Terminations and Protocol Deviations

The following rules and conventions will be used for patients who terminate from the study early or are dropped from the study because of protocol deviations.

If a patient terminates from the study early, all efforts will be made to complete Visit 7 study procedures.

Any patient who either requests to be dropped from the study because of lack of therapeutic efficacy or is dropped by the Investigator for lack of therapeutic efficacy will automatically be considered a "clinical failure" irrelevant of their target toenail assessment score at the termination visit.

Any patient who uses any protocol restricted medication specifically for the treatment of their infection will be discontinued from further participation in the study and automatically be considered a "clinical failure" irrelevant of their target toenail assessment score at the last visit.

Any patient who uses any protocol restricted medication NOT specifically for the treatment of their onychomycosis will be discontinued from further participation in the study. The patient will be considered a "clinical cure" or "clinical failure" based on the target toenail assessments at the termination visit.

Any patient who is dropped for any other reason, other than those covered above, had a positive baseline culture and makes at least one post-baseline visit where clinical assessments for target toenail are performed and/or a KOH and/or mycological culture result is obtained, will be

A Randomized, Placebo-Controlled, Double-Blind, Parallel-Group, Multi-Site Phase 2b Clinical Study to Assess the Efficacy, Safety and Tolerability of 8-Week Regimens of Novexatin[®], 10% Topical Solution (Taro Pharmaceuticals, USA, Inc.) in Patients with Mild to Moderate Onychomycosis

included in the ITT. Examples would include: failure to use the study products as required by the protocol (see section 9.4.5), patient withdraws consent for continued participation, patient fails to make study visits on a timely basis.

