9.5.7 Visit 7: Day 365 ± 14 (4 weeks post-treatment or Early Termination)

1. **Urine Pregnancy Test:** For women of childbearing potential, a urine pregnancy test will be performed to evaluate pregnancy. Any patient with a positive pregnancy test will not be allowed participation in the study.
2. **Clinical Laboratory Tests:** Blood and urine sample for safety lab tests will be taken. The tests are outlined in Appendix D.
3. **Collect/Review Patient Diary:** Collect patient diary and review for concomitant medications, adverse events and compliance with the protocol.
4. **Physical Exam:** The Investigator will perform a general physical exam for each patient and any significant findings will be noted. The physical exam, at a minimum, must include an examination of the lower extremities.
5. **Vital Signs:** BP, HR, RR and body temperature will be recorded.
6. Trimming target nail, if needed.
7. **Investigator Clinical Assessment:** Perform a foot/toenail exam. Record infected toenail count, target toenail involvement and nail appearance.
8. **Evaluation of Toenail Appearance and Condition:** The investigator and patients will perform a visual assessment and rate target toenail appearance and condition per Appendix A.
9. **Visual Assessment:** The investigator will assess the nail involvement of the “target toenail”. If the nail involvement does not reach zero at the final visit, the investigator will visually assess the nail involvement based on the following range:
 - 0%
 - > 0-5%
 - 6-9%
 - 10-35%
 - > 35%

A Randomized, Placebo-Controlled, Double-Blind, Parallel-Group, Multi-Site Phase 2b Clinical Study to Assess the Efficacy, Safety and Tolerability of 8-Week Regimens of Novexatin®, 10% Topical Solution (Taro Pharmaceuticals, USA, Inc.) in Patients with Mild to Moderate Onychomycosis

10. **Planimetry Assessment:** Appropriate photographic documentation will be obtained in accordance with Canfield Scientific Inc. guidelines for the planimetry assessment.
11. **Application Site Reactions:** The Investigator will evaluate the patient for local application site reactions and question patient regarding symptoms experienced since the previous visit based on the scale provided in Appendix C.
12. **KOH Test:** Microscopic examination of specimens of affected toe nails will be conducted to visualize the presence of pathogenic fungi. Collected nail specimens will be processed on-site for KOH slide preparation as outlined in Appendix B.

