### **Secondary Endpoints:**

1. The proportion of patients in each treatment group with a complete or almost complete therapeutic cure of onychomycosis of the target toenail assessed at each of the two test-of-cure visits (Day 141 and Day 365).
2. The proportion of patients in each treatment group with a mycological cure of the target toenail assessed at each of the two test-of-cure visits (Day 141 and Day 365).
3. The proportion of patients in each treatment group with a complete clinical cure of the target toenail assessed at each of three test-of-cure visits (Day 141, Day 281 and Day 365).
4. The proportion of patients in each treatment group with a satisfactory clinical cure of the target toenail assessed at each of three test-of-cure visits (Day 141, Day 281 and Day 365).

**Complete therapeutic cure** is defined as both complete clinical and mycological cure of the target toenail

**Almost complete therapeutic cure** is defined as both mycological and satisfactory clinical cure of the target toenail

**Mycological cure** is defined as a negative KOH test **and** a negative fungal culture.

**Complete clinical cure** is defined as 0% nail involvement.

**Satisfactory clinical cure** is defined as  $\leq 5\%$  of the target toenail involvement.

**NOVUM PHARMACEUTICAL RESEARCH SERVICES  
STATISTICAL ANALYSIS PLAN**

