Statistical testing will begin with comparison 1. If statistical significance is attained with comparison 1 ( $p < 0.05$ ), then a claim of superiority for comparison 1 can be made and the next comparison in the hierarchical evaluation scheme can be tested for statistical significance. If statistical significance is not attained for comparison 1 ( $p \geq 0.05$ ), then testing of all subsequent comparisons is stopped. The hierarchical, conditional-stepwise evaluation scheme allows for each comparison to be evaluated at the 5% level, while preserving an overall type I error rate of no more than 5%. For the proportion of patients in each treatment group with a complete and almost complete therapeutic cure, complete and satisfactory clinical cure and mycological cure of onychomycosis of the target toenail, the statistical analysis for superiority will be conducted using a two-sided Cochran-Mantel-Haenszel (CMH) exact test, stratified by clinical site, at the 5% significance level. The primary and secondary analyses will be performed using an observed case (OC) analysis in the ITT population. Patients discontinued because of lack of treatment effect will be included in the primary analysis as treatment failures.

The following two sensitivity analyses will also be performed on the primary efficacy endpoint in the hierarchical, conditional-stepwise evaluation scheme:

**NOVUM PHARMACEUTICAL RESEARCH SERVICES  
STATISTICAL ANALYSIS PLAN**

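### Rescue antifungal users are set to clinical failure only, so secondary endpoint 2 can score a clearance obtained after rescue as a mycological cure for the randomised arm

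*SAP*

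**What the plan says.** Protocol 9.3.5 and SAP 8.5 carry the same rule for rescue. The protocol begins: "Any patient who uses any protocol restricted medication specifically for the treatment of their infection will be discontinued from further participation in the study". The SAP says the patient will be "discontinued from further participation in the study and automatically be considered a 'clinical failure' regardless of their target toenail assessment score". Neither text mentions KOH, culture or mycological status.

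Secondary endpoint 2 (SAP 6) is: "The proportion of patients in each treatment group with a mycological cure of the target toenail assessed at each of the two test-of-cure visits". The protocol synopsis defines the outcome: "Mycological cure is defined as a negative KOH test and a negative fungal culture".

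SAP 8.2.1 sets the handling of missing outcomes: "The primary and secondary analyses will be performed using an observed case (OC) analysis in the ITT population". The next sentence adds: "Patients discontinued because of lack of treatment effect will be included in the primary analysis as treatment failures". That sentence concerns lack of effect, not rescue, and names only the primary analysis.

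Protocol 9.3.5 asks that early terminators complete the Visit 7 procedures. Those include a KOH test ("Collected nail specimens will be processed on-site for KOH slide preparation as outlined in Appendix B") and a culture taken whatever the KOH result. The study schematic labels Visit 7 as serving both as a test of cure and as the early-termination visit.

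**The concern.** The restricted list in Protocol 9.3.3 includes systemic antifungals such as terbinafine. A drug of that kind acts directly on the KOH and culture results that endpoint 2 measures. A patient who took one for the nail infection and then tests negative tells us about the rescue drug, yet the derivation would credit the result to Group A, B or C.

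If Novexatin works, rescue is plausibly more common on placebo. The misplaced cures would then fall mostly in Group C and shrink the mycological cure differences against placebo. Endpoint 2 is part of the hierarchical testing, and Protocol 10.6 says that the efficacy results will be used to size Phase 3. The primary endpoint is not at stake.

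**Working it through.** **1. The plan's own figure.** Inputs from Protocol 10.2: 49% v 21%, 46 per group, two-sided 5%, pooled Z test, 23% drop-out.

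- Pooled rate (0.49 + 0.21)/2 = 0.35. Null SE = √(2 × 0.35 × 0.65/46) = 0.0995.
- Alternative SE = √((0.49 × 0.51 + 0.21 × 0.79)/46) = 0.0951.
- Power = Φ((0.28 − 1.96 × 0.0995)/0.0951) = 81.5%, in line with the stated figure of over 80%.
- 46/(1 − 0.23) = 59.7, so 60 per group and 180 in total.

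The sizing reproduces. None of it depends on the rescue rule.

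**2. The rule applied to one patient.** Take a rescue user with negative KOH and negative culture at a counted visit.

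| Endpoint | Clinical component | Result under SAP 8.5 |
|---|---|---|
| Primary: complete therapeutic cure | complete clinical cure | failure |
| Secondary 1: complete or almost complete therapeutic cure | complete or satisfactory clinical cure | failure only if clinical failure also overrides satisfactory cure; not stated |
| Secondary 2: mycological cure | none | **cure** |
| Secondary 3: complete clinical cure | complete clinical cure | failure |
| Secondary 4: satisfactory clinical cure | satisfactory clinical cure | not stated |

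**3. Does another rule close the gap?**

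- The treatment-failure sentence in SAP 8.2.1 does not mention rescue users and covers only the primary analysis.
- The two sensitivity analyses apply to the primary endpoint. SAP 8.2.3 extends them to the Canfield versions of the primary endpoint and of secondary endpoints 1 and 3, not to endpoint 2. They also deal with missing results, whereas here the result is observed.
- SAP 7 keeps these patients in the ITT population, and no per-protocol population is defined.

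**4. Can a post-rescue sample reach a counted visit?**

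- Yes, without any mapping assumption, when rescue is first discovered at an in-window Visit 4 (Day 134 to 148) or Visit 7 (Day 351 to 379). KOH and culture are taken at that same visit.
- Possibly, when rescue is found earlier and the early-termination sample is treated as Visit 7. The gap between Visits 4 and 5 alone is 281 − 141 = 140 days, so rescue use could be long by then. The documents point both ways. The schematic merges test of cure and early termination, and SAP 8.5 classifies some discontinued patients from the termination visit. The sensitivity analyses, however, treat patients without an assessment at Day 365 ± 14 as missing.

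**5. Size.** One such patient moves an arm of 46 by 1/46 = 2.2 points. In the Day 141 comparison, one patient in the combined A + B group moves it by 1/92 = 1.1 points.

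For B v C at Day 365, the shift is (rescue rate in C − rescue rate in B) × k. Here k is the share of rescue users who end with a counted negative result and would otherwise have been positive. Changes in denominators are ignored. All rates below are assumptions.

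- If only in-window samples count, the main route is rescue begun in the 28 days between Visits 6 and 7. With starts spread evenly over 364 days and every such user turning negative, k = 28/364 = 0.077.
- If early-termination samples count as Visit 7, k could be much higher; 0.20 and 0.70 are shown.

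| Assumed rescue use, B / C | k = 0.077 | k = 0.20 | k = 0.70 |
|---|---|---|---|
| 0% / 4% | 0.3 points | 0.8 points | 2.8 points |
| 2% / 8% | 0.5 points | 1.2 points | 4.2 points |
| 4% / 12% | 0.6 points | 1.6 points | 5.6 points |

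**The case against.** The strongest objection is timing. B v C and A v C are tested only at Day 365, rescue users are discontinued, and medication is reviewed at every visit. Most rescue users would leave before Day 351, so if only in-window samples count, few can affect those comparisons. This stands, and it is why the first column of the second table is so small. It does not remove the gap, because the mapping of early-termination samples is open and the in-window route exists at both visits. At Day 141 the route is wider (84 days between Visits 3 and 4), but it affects only the A + B v C comparison.

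A reader might infer a large loss of power. Assuming 60% v 30% mycological cure, 46 per arm and k = 0.70, the three rescue scenarios give pooled-Z power of 75%, 70% and 65%, against 84% with no rescue. The documents do not support those figures. They give neither set of rates, the value of k presupposes that nearly all rescue users have a counted sample, SAP 8.7 replaces the Z test with a site-stratified exact CMH test, and no power is claimed for endpoint 2.

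A reader might also extend the point to lack-of-efficacy dropouts, for whom SAP 8.5 says a patient who "is dropped by the Investigator for lack of therapeutic efficacy will automatically be considered a 'clinical failure' regardless of their target toenail assessment score". Those patients need not have taken any antifungal. A negative KOH and culture is then a valid result on randomised treatment, and clinical and mycological cure are deliberately separate endpoints. Overriding it is a choice of estimand rather than a correction.

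Nor do the documents show that a rescue user fails all four other endpoints. As the first table shows, that is unstated for secondary endpoints 1 and 4.

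Finally, if rescue is more common on placebo, the bias runs toward no difference and would not create a false superiority claim over placebo. That also stands, and it limits the consequence.

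**Conclusion.** The gap is real and confined to rescue users under secondary endpoint 2. As written, the plan scores a negative KOH and culture obtained after rescue antifungal use at a counted visit as a mycological cure. The primary endpoint is protected and the sample size is unaffected.

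The size cannot be fixed from the documents. Under the assumptions shown, the Day 365 difference shifts by well under 1 point if only in-window samples count, and by roughly 1 to 6 points if early-termination samples are carried to Visit 7. The direction rests on the further assumption that rescue is more common on placebo. This is a cheap improvement to one secondary endpoint of a Phase 2b trial, not a threat to the main conclusion.

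**What to change.** In SAP 8.5, before unblinding:

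- State that patients who use restricted medication for the nail infection count as failures for every efficacy endpoint, expressly including mycological cure and satisfactory clinical cure, at every test-of-cure visit on or after the date of first use. Later KOH and culture results are listed but not counted as cures.
- State whether an early-termination sample outside Day 365 ± 14 counts as Day 365.
- Leave lack-of-efficacy dropouts who took no antifungal on their observed KOH and culture results for endpoint 2.
- Record the change in SAP 8.7.

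This alters the classification of outcomes only and leaves patient management as it is. It costs a few sentences and a change to the endpoint derivation. Medication dates and indications are already in the concomitant medication listing. That listing's shell shows a partial start date, so a convention for such dates is needed.

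Two effects should be disclosed. Rescue users who would be missing at a later visit, and so left out of the observed-case analysis, become failures; if they are more common on placebo, this favours active treatment. And a patient who had truly cleared before rescue counts as a failure from then on.
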